1. INTRODUCTION

Low back pain (LBP) is reported by approximately 20% of North Americans, the majority of whom experience both pain and physical impairment (1, 2). Patients with chronic LBP have an increased utilization of medical services, and higher incidence of lost workdays and long-term disability, representing a significant burden to the healthcare system and the economy (1-3).

It has been estimated that up to 84% of people will experience an episode of acute LBP in their lifetimes (4), and recovery rates range from 39% to 76% (5, 6). The neurobiological mechanisms underlying recovery or persistence of the condition remain to be understood, and identification of such mechanisms would allow early intervention, interruption, and prevention of progression to a chronic state.

The existence of a platform for the continuous enrolment of LBP patients to which pain researchers would have access would greatly facilitate the investigation of key research questions including what factors (e.g. genetic, epigenetic, neurobiological, biomechanical, psychological) contribute to the transition from acute to chronic LBP, how these factors might change with time as pain progresses, and what are the health care utilization and medication patterns associated with that progression.

The Quebec Pain Research Network has developed a Strategic Initiative funded by the FRQS to the QPRN to facilitate research on chronic LBP. The QPRN LBP Scientific Committee has been meeting regularly since 2015 to develop this shared vision. The committee includes experts from throughout the province in physical therapy, neurobiology, psychology, genetics, epigenetics, physicians, chronic pain perspective partners and a full time scientific coordinator. Please see Appendix 1 for further details on The Team.

The current proposal is designed to establish a province-wide online database for longitudinal studies of individuals with LBP (The Core). The Core Database will not only be a valuable research tool itself, but we will use The Core to facilitate recruitment for a series of affiliated projects, including a biobank that will be covered under an independent protocol but integrated with The Core.

2. OBJECTIVE

SPECIFIC AIM 1 (Tier 1) - Develop a province-wide, community-based, longitudinal cohort of individuals initially reporting acute LBP to achieve a comprehensive biopsychosocial understanding of factors underlying LBP trajectories.

SPECIFIC AIM 2 (Tier 2) - Build capacity in acute and chronic LBP research through integration of hypothesis-driven satellite projects.

3. DESCRIPTION OF STUDY POPULATION. *The QLBPS will enroll adult women and men with self-reported LBP.*

3.1 Inclusion Criteria for potential LBP participants

1. At least 18 years old;
2. Internet access;
3. Fluent in English or French;
4. Self-reported LBP.

3.2 Exclusion Criteria for potential LBP participants

No exclusion criteria will be adopted in this study. *Note: While our recruitment efforts will focus on the acute or subacute phases, previous experience suggests that individuals with chronic LBP (cLBP) will also respond. While not the focus of the Study, their longitudinal data will be valuable and affiliated projects may be interested in also recruiting cLBP participants. We will therefore accept all individuals who self-register for the study and will then filter the data based on specific research questions.*

4. RECRUITMENT AND ENROLLMENT *A flowchart describing all study procedures is provided in Appendix 2. These procedures are described in detail below.*

4.1 Recruitment strategy A broad recruitment strategy (initially limited to the Montreal area, but ultimately aimed at all major urban areas in the province of Quebec and Canada), is planned for the QLBPS and may include advertisement in newspapers, public means of transportation, social media such as Facebook and through list servers, patient advocacy organizations or professional societies, unions of workers at risk for LBP and medical populations.

Consent Advertisements will contain the electronic address to the **QLBPS Landing Page**, which will be accessible through to the Quebec Pain Research Network (QPRN) website.

4.2 The Landing Page will ask the participant if he has back pain and to indicate his postal code, sex, age (to evaluate the relevance of our advertising and adjust if necessary) and if he is interested in participating to research.

Participants at this point will receive an email inviting them to access the **Baseline Online Survey**.

This email will also include a link to the informed consent form.

Once on the baseline online survey, 3 questions will be asked :

Question 1: I have read the information about the study in the previous email and I agree to participate in the study: Yes/No. If No, the website will post “Thank you for your time”. If Yes, individuals will be asked **Question 2:**

Question 2: I accept to be contacted regarding participation in additional studies: Yes/No
The answer will be recorded in the core database and will be used to filter participants that may be contacted in the future by other QPRN-approved Investigators.

Question 3: I would consider donating blood: Yes/No.

4.3 Enrolment At the completion of the 3 Questions, individuals who answered Yes to Question 1 (regardless of answers 2 or 3) are enrolled in the study.

After the participant has consented to be contacted for other studies, the researchers that had their project approved by the QLBP scientific committee and the McGill University ethics committee will be able to contact selected participants. The research projects must meet the following conditions in order to be granted access to contact participants:

- The research project must coincide with the objective of the Bank;
- The research project must have scientific value and be scientifically sound;
- The research project must be presented and performed by qualified researchers.
- The research project must be approved by a duly constituted REB.

5. EXPERIMENTAL PROCEDURES QLBP Study participants will be asked to complete the following Surveys.

5.1 Baseline Online Survey After consenting to participate in the QLBP, participants will gain access to the following set of online questionnaires available in English and French:

1. PERSONAL INFORMATION SURVEY (Appendix 5). Personal information such as date of birth, sex, gender, race and geographic region. The section will also ask the participant for permission to access their medical data through the Régie de l'assurance maladie du Québec (RAMQ).
2. QUEBEC LOW BACK PAIN CORE DATASET. The content of the QLBP Core Dataset was

developed by the Quebec Pain Research Network, Low Back Pain Consortium Scientific Committee using an Iterative consensus-building process (Appendix 6).

- **CHARACTERIZATION SURVEY:** A set of 6 questions that allow us to classify all participants into acute or chronic LBP according to agreed-upon definitions.
- **CANADIAN MINIMUM DATASET FOR RESEARCH STUDIES ON LOW BACK PAIN.** The Canadian dataset was adapted from the recommendations of the NIH task force on research standards for chronic LBP in order to advance the field, solve controversies, and facilitate future research. This questionnaire assesses core domains recommended by IMMPACT, namely pain frequency and intensity, physical and emotional functioning, as well as it collects detailed demographic and general health measures, and has been culturally adapted and translated to be used for low back pain for research among English and French-speaking populations in Canada.
- DN4 (validated questionnaire assessing the neuropathic component of chronic pain)
- EQ-5D-5L (validated questionnaire for overall quality of life)
- Other medical conditions

Completion of all questionnaires is expected to take no more than 30 minutes. Those who self-enroll in the QLBPSS but do not complete all abovementioned questionnaires will be contacted by the study coordinator by phone and/or e-mail to be reminded to complete the surveys.

5.2 Follow-up Online Surveys At 3, 6, 12, and 24 months after completing the baseline online procedures, participants will complete follow-up survey online. At each of these time points, participants will receive an e-mail with a link to complete the questionnaires listed below.

1. QUEBEC LOW BACK PAIN CORE DATASET
2. PATIENT GLOBAL IMPRESSION OF CHANGE (PGIC) (Appendix 7)

Completion of all questionnaires is expected to take no more than 30 minutes. At each time-point, participants who do not complete all abovementioned questionnaires will be contacted by the study coordinator by phone and/or e-mail to be reminded of completing them.

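### Follow-up non-responders are only reminded to complete the full survey, so their back-pain status stays missing; if recovered participants answer less often, persistence would be overstated

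*Protocol*

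**What the plan says.** Protocol section 5.2 sets the follow-up schedule: "At 3, 6, 12, and 24 months after completing the baseline online procedures, participants will complete follow-up survey online". The content each time is the whole Core Dataset plus a global impression of change, and the stated burden is an upper limit: "Completion of all questionnaires is expected to take no more than 30 minutes".

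For those who do not finish, section 5.2 gives one step, at each time point: "participants who do not complete all abovementioned questionnaires will be contacted by the study coordinator by phone and/or e-mail to be reminded of completing them". The available text names no short outcome question, no option to take answers during the contact, no number of reminders, and no expected response rate.

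Two other places bear on this. Aim 1 (section 2) is to "achieve a comprehensive biopsychosocial understanding of factors underlying LBP trajectories" in people who first report acute pain. The Introduction says that "recovery rates range from 39% to 76" per cent.

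**The concern.** Whether back pain is still present at each time point defines a trajectory, so it is the outcome on which Aim 1 turns. By the protocol's own cited range, recovered people will be a large share of the acute cohort at follow-up. They receive the same back-pain survey as people still in pain and plausibly have less reason to complete it. If they do answer less often, missingness depends on the outcome itself and the observed share with persistent pain is too high.

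This is a matter of data collection. An analysis plan can weight, impute or run sensitivity analyses, but it cannot recover a status that nobody asked for. Section 5.2 already plans a contact with these participants, and as written that contact does not collect the outcome.

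**Working it through.** **Inputs from the protocol.** Recovery r = 39% and 76% (Introduction), so true persistence p = 1 - r = 61% and 24%. The Introduction does not say at what time these rates apply; they are used here as a range. The protocol states no sample size, response rate or dropout figure, so there is no figure of its own to reproduce.

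**Assumed inputs.** Response a if pain persists and b if recovered. The protocol gives neither, so a range is shown, including equal and reversed response.

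**Formula.** Observed persistence = p·a / (p·a + r·b). The bias depends only on the ratio b/a.

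**Worked case, a = 80%, b = 60%.**
- r = 39%: 0.61 × 0.80 = 0.488; 0.39 × 0.60 = 0.234; 0.488 / 0.722 = 67.6%, or +6.6 points.
- r = 76%: 0.24 × 0.80 = 0.192; 0.76 × 0.60 = 0.456; 0.192 / 0.648 = 29.6%, or +5.6 points.

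**Range.**

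| Response: persistent / recovered | Observed when truth is 61% | Observed when truth is 24% |
|---|---|---|
| equal | 61.0% (0) | 24.0% (0) |
| 80% / 70% | 64.1% (+3.1) | 26.5% (+2.5) |
| 80% / 60% | 67.6% (+6.6) | 29.6% (+5.6) |
| 80% / 50% | 71.4% (+10.4) | 33.6% (+9.6) |
| 80% / 40% | 75.8% (+14.8) | 38.7% (+14.7) |
| 60% / 80% (reversed) | 54.0% (-7.0) | 19.1% (-4.9) |

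**Associations.** Let response be π(y, x) for outcome y and factor x. The observed odds ratio is the true one multiplied by π(1,1)·π(0,0) / [π(1,0)·π(0,1)]. If response depends on outcome alone, or is a product of an outcome term and a factor term, this multiplier is 1 and the odds ratio is unchanged. It differs from 1 only when outcome and factor act on response jointly, beyond that product.

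**Effect of a short outcome at the reminder.** Suppose it reaches a share f of non-responders, assumed equal in both groups. Response becomes a + f(1 - a) and b + f(1 - b). Starting from 80% / 50%, the overstatement at r = 39% / 76% is:

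| Share reached | Overstatement (points) |
|---|---|
| none | 10.4 / 9.6 |
| 25% | 7.0 / 6.0 |
| 50% | 4.2 / 3.5 |
| 75% | 1.9 / 1.5 |

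For f = 50%, response becomes 90% / 75%. At r = 39% this gives 0.61 × 0.90 = 0.549; 0.39 × 0.75 = 0.2925; 0.549 / 0.8415 = 65.2%, or +4.2 points.

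**The case against.** A reader might infer that recovered participants are in fact lost selectively and that persistence is in fact overstated. The protocol does not support that. It gives no response rate by outcome, equal response gives no bias, and the sign reverses if people in pain or disabled drop out more. That objection stands, so the point is conditional.

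A reader might also infer that nothing is known about non-responders. That goes too far. Those who completed baseline have pain, function, quality-of-life and demographic data (section 5.1). Intermittent non-responders may be seen at other waves. Linkage to administrative and pharmacy data (section 6.2) does not depend on answering the survey. These sources support a comparison of responders with non-responders. Linkage depends on permission, however, and none of the three measures pain or recovery at the missed time point.

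It can further be said that Aim 1 concerns factors, not a persistence rate, and that self-registered volunteers were never meant to yield a population rate. This is fair: outcome-dependent response by itself leaves odds ratios intact. What remains is the case where response depends jointly on outcome and factor, which cannot be checked without outcomes from some non-responders.

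Finally, the 30 minutes is a maximum, and the reminder also covers partial completers, some of whom may already have given their pain status. The appendices, including the procedure flowchart and the Core Dataset itself, are not in the available text, nor is anything between sections 6 and 9. The statement that a reminder is the only step therefore applies to the text at hand.

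**Conclusion.** The point holds in conditional form. As section 5.2 reads, a person who does not answer is asked again for the full set and, if the reminder fails, the outcome for that time point is missing. Should recovered participants respond less, observed persistence would be too high by about 3 to 15 points over the assumed response ratios of 0.875 to 0.5 (recovered to persistent). With 80% against 60% it is 5.6 to 6.6 points. The size rests wholly on assumed response rates. Bias in associations needs the further assumption of joint dependence on outcome and factor, and no size can be given for it.

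Nothing in the section is false or contradictory. This is an inexpensive improvement to data collection, worth making because it would also show whether response differs by outcome at all.

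**What to change.** Amend section 5.2 so that at the final reminder contact, by phone or e-mail, the coordinator offers a minimum outcome set: low back pain now (yes/no), average intensity in the past week (0 to 10), and the month it stopped if gone. State which reminder is the final one, since the protocol sets no number. Record the mode of collection, use these answers as follow-up outcomes for Aim 1, and compare those who gave them with full responders.

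The cost is about a minute on a contact already planned, a mode field in the database, and a short script or form for ethics approval. The downsides are a possible mode effect (phone against web) and some people giving the short form in place of the full survey; offering it only at the last reminder limits the second. Bias remains among those never reached, and the gain is smaller than tabulated if recovered people are also harder to reach.

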6. DETAILS ON CONFIDENTIALITY

6.1 Confidentiality, de-identification and transfer

Confidentiality Participant confidentiality will be strictly held in trust by the investigators, study staff, and the representatives of McGill University and the MUHC-RI (where the data is held). This confidentiality is extended to cover testing of biological samples and genetic tests in addition to any study information relating to participants.

Data transfer Data transfers will only be done to researchers who a) obtain ethical approval to access the QLBPS data through their home IRB's and b) approval of the scientific committee of the QPRN LBP Consortium.

For the purposes of recruitment to subprojects, basic information including email and phone number, age, sex, duration of low back pain will be shared with approved subproject investigators ONLY if the participant has agreed to be contacted by other studies. In the event that a participant is ultimately recruited to a subproject and signs the corresponding consent, the PI of the subproject will have access to The Core Database information for those individuals only, by request.

6.2 Health Care information

Participants are asked to provide their unique health insurance number to allow the linkage between patient-reported outcomes and Quebec administrative databases. [name] (Université du Québec en Abitibi-Témiscamingue) will be the sole designated researcher responsible for the analysis and conservation of such administrative data and will submit an application for approval at the Commission d'accès à l'information du Québec and Régie de l'assurance maladie du Québec. This information will also be sent to reMed, a research team that automatically receives data on medications from electronic service providers of community pharmacies so that patients can be reimbursed for their insurance claims. All transfers of information will be done via registered mail and secured electronic files.

